6.5.3. Other Assessments

Additional scans, including brain scans, or nuclear medicine bone scan may be performed if clinically indicated (eg, symptoms of brain metastasis) at the discretion of the Investigator.

6.5.4. Assessment of Response According to Immune-Related Response Criteria (irRECIST)

Evaluation of response will also be performed using irRECIST guidelines as an exploratory, but not treatment-determining, assessment. Evaluation via irRECIST will begin if treatment is continued beyond RECIST 1.1 documented progression. Additional details and definitions of irRECIST are found in Appendix C in Section 18.3.

6.6. Pharmacokinetics

Plasma/serum samples will be collected to assay plasma concentrations of CC-122 and nivolumab.

On PK sampling days, dosing and sample collection information including dosing date, dosing time (24 hour clock), and actual PK blood sampling time (24 hour clock) should be accurately documented on the appropriate electronic case report form (eCRF) pages.

6.6.1. Pharmacokinetics of CC-122

Pharmacokinetic samples will be collected during the dose escalation part. No PK will be collected during the dose expansion part.

Dose Escalation Part (all subjects): Cycle 1 Day 15: predose (-30 to -5 minutes prior to CC-122 dose), 0.5 hour (\pm 5 minutes), 1 hour (\pm 10 minutes), 2 hours (\pm 10 minutes), 4 hours (\pm 10 minutes), and 8 hours (\pm 60 minutes) after administration of CC-122.

On C1D15, subjects will be asked NOT to take CC-122 at home. CC-122 will be administered to these subjects at the study center after the collection of the predose PK blood sample. For convenience, on PK collection days CC-122 should be administered first, followed by nivolumab.

6.6.2. Pharmacokinetics of Nivolumab

Pharmacokinetic samples will be collected during the dose escalation part. No PK will be collected during the dose expansion part.

Dose Escalation Part (all subjects): Predose (-30 to -5 minutes prior to nivolumab dose) and end of infusion on C1D1 and C1D15.

6.7. 12-lead Electrocardiograms

Triplicate 12-lead ECGs will be recorded at the visits listed in Table 3 and assessed centrally. The 12-lead ECGs (12-lead at 25 mm/second reporting rhythm, ventricular rate, PR-interval, QRS complex, QT interval, and QTcF interval) will be performed after the subject has been in the supine position for at least 5 minutes.

Triplicate ECGs (3 recordings within 2 ± 1 minute intervals) will be performed at the following time points:

- Screening
- Cycle 1, Day 1 - Predose (0 hour; within 90 minutes prior to CC-122 dosing)

- [REDACTED]

[REDACTED]

■ [REDACTED]

[REDACTED]

[REDACTED]

■ [REDACTED]

[REDACTED]

[REDACTED]

[REDACTED]

[REDACTED]

[REDACTED]

■ [REDACTED]

[REDACTED]

6.9. CC-122 Risk Counseling Prior to Dosing

CC-122 Pregnancy Risk Minimization Plan for Celgene Clinical Trials (Appendix G, Section 18.7) applies to all subjects receiving CC-122 therapy.

CC-122 will be dispensed through a qualified healthcare professional (including but not limited to, nurses, pharmacists and physicians). These healthcare professionals will be trained by Celgene, or designee, in requirements specific to counseling of subjects. Once trained these healthcare staff will counsel subjects prior to the administration of CC-122 to ensure that the subject has complied with all requirements including use of birth control and that the subject understands the risks associated with CC-122. This step will be documented with a completed Education and Counseling Guidance Document, and CC-122 will not be administered until this step occurs.

A CC-122 Information Sheet will be provided to each subject before IP is dispensed.

Females of childbearing potential and fertile males, other than the subject, should not handle or administer CC-122 unless they are wearing gloves.

7. DESCRIPTION OF STUDY TREATMENTS

7.1. Description of Investigational Product(s)

7.1.1. CC-122

CC-122 will be supplied by Celgene Corporation. CC-122 is available as a 1.0 mg formulated capsule (equivalent to 1.13 HCl), 2.0 mg formulated capsule (equivalent to 2.254 HCl), 2.5 mg formulated capsule (equivalent to 2.818 HCl), 3.0 mg formulated capsule (equivalent to 3.38 HCl), 3.5 mg formulated capsule (equivalent to 3.95 HCl), and 4.0 mg formulated capsule (equivalent to 4.51 mg HCl). Each formulated capsule is provided in reddish brown gelatin capsules, containing the following excipients: Avicel PH 102, spray dried mannitol, crospovidone, aerosil and stearic acid.

7.1.2. Nivolumab

Nivolumab 100 mg vials (10 mg/mL) will be supplied by Celgene Corporation and labeled appropriately as investigational material for this study. Nivolumab vials must be stored in the refrigerator at 2°C to 8°C, protected from light and freezing.

7.2. Treatment Administration and Schedule

The study is designed to explore three dose levels of CC-122 to identify the RP2D, and is not required to escalate to a NTD or MTD. CC-122 will initially be administered orally 5 consecutive days out of 7 (5 days on/2 days off weekly) on Days 1 to 5, 8 to 12, 15 to 19 and 22 to 26 of each 28-day cycle. The investigated starting daily dose of CC-122 will be 2.0 mg, and two subsequent dose levels (3.0 and 4.0 mg) are planned to be evaluated as described in [Table 4](#), based on pre-specified DLTs. Intermediate dose levels, or a higher dose level, may be evaluated at the discretion of the Safety Review Committee (SRC). Dose escalation to intermediate or higher dose levels of CC-122 will not exceed 50% of the previously established tolerable dose level. Smaller dose increments based on toxicity, PK profile and PD findings may be evaluated, if necessary. Nivolumab will be administered at the dose of 3.0 mg/kg IV every 2 weeks. Once the RP2D for dosing of CC-122 in combination with nivolumab is defined, expansion (Phase 2) will start. Investigational products will be administered for up to 2 years.

7.2.1. Dose Levels

Dose levels to be explored are shown in [Table 4](#).

Table 4: Dose Levels

Dose Level	CC-122 Dose (mg)	CC-122 Schedule (days)	Nivolumab Dose (mg/kg)	Nivolumab Schedule
- 1	1.0	5/7	3.0	Every 2 weeks
1	2.0	5/7	3.0	Every 2 weeks
2	3.0	5/7	3.0	Every 2 weeks
3	4.0	5/7	3.0	Every 2 weeks

Dosing will start at dose level 1. Each dose level must be cleared by the SRC based on review of all available clinical, safety, PK, PD and laboratory data before initiating the next higher dose level. The study intends to identify the RP2D at or below the 4.0 mg dose level, however intermediate or higher dose levels may be explored at the discretion of the SRC.

During dose escalation, the decision to either evaluate a higher dose level, an intermittent dose schedule, or declare the RP2D (or if applicable NTD) will be determined by the SRC, based on their review of all available clinical data, PK, PD and laboratory safety data for a given dose cohort.

Intra-subject dose escalation of CC-122 is not permitted during Cycle 1, but may be permitted in later cycles if approved by the SRC.

Dose reduction of CC-122 and temporary interruption of one or both IPs due to toxicity during Cycle 1 is allowed but may constitute a DLT, as outlined in Section 7.6 and 7.9.

Study treatment may be discontinued if there is evidence of clinically significant disease progression, unacceptable toxicity or subject/physician decision to withdraw. Subjects may continue to receive CC-122 and nivolumab beyond disease progression at the discretion of the Investigator.

If any subject continues to experience unacceptable toxicity after permitted IP adjustments, one or both IPs will be discontinued permanently.

The estimated total number of subjects to be enrolled during dose escalation is approximately 20 to 30, depending on cohort size. Up to 30 additional subjects will be evaluated for safety, PK, PD, and preliminary anti-tumor effects in one or two expansion cohorts.

7.3. Definition of a DLT Evaluable Subject

All subjects who receive at least one dose of either CC-122 or nivolumab will be evaluable for DLT.

In the dose escalation part, a subject evaluable for DLT is defined as one who:

- Received at least 75% of the planned doses of CC-122 and of nivolumab during Cycle 1 without experiencing a DLT, having been followed for the entire DLT assessment period (see Section 7.6)
- or
- Experienced a DLT after receiving at least one dose of either IP.

Non-evaluable subjects will be replaced at the discretion of the SRC. Additional subjects within any dose cohort may be enrolled at the discretion of the SRC.

7.4. Definition of Non-tolerated Dose

An NTD is defined as a dose level at which 2 or more out of up to 6 evaluable subjects in any dose cohort experience a DLT in Cycle 1. Escalation to an NTD is not required in this study, as described in Section 7.2

7.5. Definition of Maximum Tolerated Dose (MTD)

If an NTD is identified, dose escalation will be stopped. The MTD is defined as the last dose level below the NTD with none or 1 out of 6 evaluable subjects experiencing DLT during Cycle 1. The RP2D may be a dose that meets the definition of MTD, however escalation to an MTD is not required in this study, as described in Section 7.2.1

7.6. Definition of Dose-Limiting Toxicity

During dose escalation, the DLT assessment period is defined as Days 1 to 28 of Cycle 1 including the predose assessments specified for Day 1 of Cycle 2.

National Cancer Institute Common Terminology Criteria for Adverse Events (NCI CTCAE) Version 4.03 are used as a guide for the grading of severity of adverse events.

A DLT is defined as any of the following toxicities occurring within the DLT assessment window unless the event can clearly be determined to be unrelated to the drug. Dose-limiting toxicities are described below:

- Any toxicity that would lead to dose reduction or discontinuation of CC-122 or discontinuation of nivolumab during Cycle 1.
- Any Grade 4 non-hematologic toxicity of any duration.
- Any clinically relevant non-hematologic toxicity that is \geq Grade 3 except for:
 - Grade 3 diarrhea or vomiting of not more than 5 days duration (with optimal medical management)
 - Grade 3 fatigue or asthenia of not more than 3 days duration with optimal medical management
- Grade 3 infusion-related reaction controlled by interruption of the infusion and medical management Any liver enzymes elevation according to the definitions below:
 - AST or ALT ≥ 8 x ULN of > 7 days duration
 - Total bilirubin ≥ 5 x ULN of > 7 days duration
 - Concurrent AST or ALT > 3 x ULN and total bilirubin > 2 x ULN
- Hematological toxicities during Cycle 1 as follows:
 - Grade 4 neutropenia lasting > 7 days
 - Febrile neutropenia
 - Grade 4 thrombocytopenia lasting > 48 hours
 - Grade 3 or 4 thrombocytopenia with clinically significant bleeding
- Any \geq Grade 2 uveitis or eye pain that does not respond to topical therapy and does not improve to Grade 1 severity within the re-treatment period (≤ 6 weeks and/or prior to next nivolumab dose), or requires systemic treatment.

- Any \geq Grade 2 pneumonitis or interstitial lung disease that does not resolve with dose delay and systemic steroids. The management algorithm for pneumonitis or pulmonary toxicity can be found in the current nivolumab SmPC and in Appendix H.

Repeat laboratory assessments are required to confirm the duration of time-bound DLT criteria.

Isolated laboratory changes without associated clinical signs or symptoms (eg, hypomagnesemia, hypermagnesemia, hypoalbuminemia, hypophosphatemia, lymphocyte count increased or decreased) may not be included in this definition. These findings will be discussed and reviewed by the SRC.

Events meeting the DLT definition occurring beyond the first cycle will be taken into account when determining the RP2D. Any AE with the potential to become a DLT based on the duration should be followed appropriately to accurately determine the duration of the event.

Subjects should delay/interrupt or discontinue treatment if they experience any adverse event, laboratory abnormality or intercurrent illness (regardless of causality) which, in the opinion of the investigator, presents a substantial clinical risk to the subject with continued dosing of any IP. Such delay/interruption or discontinuation, however, will not be considered a DLT unless it meets at least one of the DLT criteria defined above or if deemed dose-limiting by the SRC.

7.7. Method of Treatment Assignment

An integrated response technology (IRT) will be used to track subject assignments to the dose levels.

7.8. Criteria for Dose Escalation

The SRC will make dose escalation decisions. The decision criteria for dose escalation are:

- If no DLT is observed in the first 3 evaluable subjects during the first cycle, dose escalation to the next higher dose level may occur.
- If 1 out of 6 evaluable subjects experiences DLT during the first cycle, dose escalation to the next higher dose level may occur. Additional subjects will be enrolled to expand the cohort to 6 evaluable subjects if less than 6 subjects are evaluable when the DLT is observed.
- If 2 or more out of up to 6 evaluable subjects experience a DLT during the DLT assessment period in a cohort, any further recruitment into that cohort will cease and this dose will be defined as an NTD.
- The SRC will determine if additional subjects will be enrolled in a parallel or at lower dose cohorts to have 6 evaluable subjects in order to define RP2D, or whether an intermediate dose level or an intermittent dosing schedule will be explored in up to 6 newly enrolled subjects. Additional subjects may be added at a given dose level to further assess the safety and/or PK.

Based on above criteria, if no DLT is observed in at least 3 evaluable subjects, the SRC may decide to escalate the dose to the next cohort.

If one DLT occurs prior to a decision by the SRC to dose escalate, the cohort will be expanded to enroll 6 evaluable subjects in total. Subjects 4 to 6 may be enrolled concurrently with the first 3 subjects if complete 28-day toxicity data are not yet available for the first 3 subjects.

If 1 subject out of 6 evaluable subjects experiences a DLT, the dose will be escalated in the next cohort, unless there are other safety considerations by the SRC. The dose may also be declared the RP2D.

The number of cohorts depends on incidence of DLT. A subject may experience more than 1 DLT. Dose escalation decisions are based on the number of subjects experiencing DLT events.

Intra-subject dose escalation beyond the dose initially assigned to a subject is not permitted in Cycle 1. Those continuing to take IP beyond Cycle 1, following approval by the SRC, may have the dose level increased providing the alternative dose level has been shown to be well tolerated by at least one cohort of other subjects in this study.

7.8.1. Definition of Stopping Criteria for Dose Escalation

Dose escalation stops when 2 or more out of up to 6 evaluable subjects at any dose level experience DLT, or when the RP2D is declared.

7.9. Permitted IP Adjustments

CC-122 dose reductions are permitted in any cycle, including Cycle 1; however in Cycle 1 this may constitute DLT. No dose reductions are allowed for nivolumab.

- Any toxicity, unless the event can clearly be determined to be unrelated to the IPs, should be managed according to the following tables.
- In the absence of clear alternative causes of liver enzyme abnormalities meeting DLT criteria, both IPs should be held and/or discontinued.
- Any treatment-related toxicity that leads to dose reduction or discontinuation of CC-122 or discontinuation of nivolumab that occurs in Cycle 1 during dose escalation will constitute DLT.
- Subjects will be allowed to continue with CC-122 at a reduced dose.

Allowed dose reductions for CC-122 are described in [Table 5](#).

For CC-122, dose reductions below 1.0 mg are not allowed.

Table 5: Allowed Dose Reductions

CC-122 Starting Dose	First Reduction	Second Reduction
1.0 mg (5/7)	NA	NA
2.0 mg (5/7)	1.0 mg (5/7)	NA
3.0 mg (5/7)	2.0 mg (5/7)	1.0 mg (5/7)
4.0 mg (5/7)	3.0 mg (5/7)	2.0 mg (5/7)

5/7 = 5 out of 7 days; NA = not applicable.

- CC-122 may be dose reduced at the discretion of the investigator and based on guidelines in Section 7.10.
- If any subject continues to experience unacceptable toxicity after the dose reductions described above one or both IPs will be discontinued permanently.
- Once CC-122 dosage has been reduced, it can be escalated when toxicity reaches \leq Grade 1. If toxicity recurs at the higher dose, the dose will be reduced a second time, but no re-escalation is then permitted.

7.10. Criteria for CC-122 Dose Reduction

Any IP-related toxicity meeting the definition of DLT will require dose reduction and/or interruption. The criteria for dose reduction listed in Table 6 and Table 7 should be used for dose modifications.

Chronic Grade 2 toxicity may warrant dose reduction of CC-122. It is recommended that such cases be discussed with the Sponsor before changes are made.

Table 6: Dose Adjustment Guidelines for CC-122 Related Non-hematologic Toxicities

Toxicity	Action
AST or ALT \geq 8 x ULN, OR Total bilirubin \geq 5 x ULN, OR Concurrent AST or ALT > 3 x ULN and total bilirubin > 2 x ULN	
 • Hold CC-122 until laboratory values return to baseline and management with corticosteroids, if needed, is complete • Reintroduce CC-122 at the same or to the next lower dose level, if available, depending on whether toxicity meets DLT criteria (Section 7.6)
Grade 4 liver enzyme or bilirubin elevation or clinical liver failure	
 • Permanently discontinue CC-122
If recurrence of Grade 3 event after dose-reduction	
 • Reduce dose to the next lower dose level; if available.
If recurrence of Grade 4 event after dose reduction	
 • Discontinue CC-122
Any non-hematological toxicity requiring interruption for > 4 weeks	
 • Discontinue CC-122

Table 6: Dose Adjustment Guidelines for CC-122 Related Non-hematologic Toxicities (Continued)

Toxicity	Action
Troponin-T > ULN with associated 20% increase in BNP over baseline with an absolute value > 100 pg/mL (confirmed on repeated measurements) without associated cardiac symptoms or findings	
 • Hold CC-122 • Cardiology evaluation, notify Sponsor • Follow troponin-T, BNP, and ECG at least every 7 days • If troponin-T returns to normal levels in ≤ 7 days and there are no other significant cardiac findings, restart CC-122 at next lower dose level or same dose • If troponin-T elevation persists beyond 7 days or recurs upon rechallenge, permanently discontinue CC-122
Troponin-T > ULN with cardiac symptoms or significant changes in ECG or LVEF	
 • Discontinue CC-122, notify Sponsor
Rash Grade 1	
 • Management with topical corticosteroid creams and/or oral antipruritic as clinically indicated.
Rash Grade 2	
 • Continue therapy if involvement of < 30% of body surface area, are asymptomatic or toxicity can be managed with topical corticosteroid creams and antipruritics. • If rash does not meet the above criteria, hold CC-122 and initiate treatment with topical corticosteroids. 
 ○ Consider systemic corticosteroids if rash does not improve to \leq Grade 1 in ≤ 7 days.
Rash \geq Grade 3	
 • If Grade 3 hold CC-122 until recovery to Grade ≤ 1. • If AE resolution to Grade ≤ 1 occurs ≤ 8 days, reintroduce CC-122 at the same dose level • If AE resolution to Grade ≤ 2 or > 7 days, reintroduce CC-122 on lower level, if available • Discontinue CC-122 for 2nd occurrence of \geq Grade 3 rash • For desquamating (blistering) Grade 3 or any Grade 4 rash, discontinue CC-122 • For maculopapular, acneiform, or pustular rashes lasting ≤ 7 days medical management is warranted

Table 6: Dose Adjustment Guidelines for CC-122 Related Non-hematologic Toxicities (Continued)

Toxicity	Action
Peripheral neuropathy (neuropathies which begin or worsen while on study) ≥ Grade 3	
 • Hold CC-122 at Investigator’s discretion • When the toxicity resolves to ≤ Grade 2 or to baseline, restart CC-122 at the next lower dose level
Allergic reaction or hypersensitivity ≥ Grade 3	
 • Discontinue CC-122
Venous thrombosis / embolism ≥ Grade 3	
 • Hold CC-122 and start anticoagulation; restart CC-122 at Investigator’s discretion (maintain dose level)
Pneumonitis Grade 2	
 • Hold CC-122 and nivolumab (see Table 8), consider corticosteroids • Restart CC-122 at next lower dose level once completely resolved
Pneumonitis ≥ Grade 3	
 • Discontinue CC-122 and nivolumab (see Table 8) • Corticosteroids recommended until symptoms resolve
Tumor flare reaction (TFR) Grades 1-2	
 • Continue CC-122, maintain dose level • NSAIDs and/or narcotics may also be used as per investigator’s discretion • Initiate therapy with corticosteroids at the Investigator’s discretion
Tumor flare reaction (TFR) Grades 3-4 (severe – disabling)	
 • Hold CC-122 • Initiate therapy with corticosteroids • NSAIDs and/or narcotics may also be used per Investigator’s discretion • When symptoms resolve ≤ Grade 1, restart CC-122 at the same dose level
Other ≥ Grade 3	
 • Hold CC-122 at Investigator’s discretion • When the toxicity resolves to ≤ Grade 2, restart CC-122 at the same dose level or the next lower dose level at Investigator’s discretion

AE = adverse event; BNP = brain natriuretic peptide; ECG = electrocardiogram; IP = investigational product; LVEF = left ventricular ejection fraction; NSAID = nonsteroidal anti-inflammatory drug; ULN = upper limit of normal.

Table 7: Dose Adjustment Guidelines for CC-122 Related Hematologic Toxicities

Toxicity	Action
Grade 2 thrombocytopenia	
 No action
Grade 3 thrombocytopenia	
 Hold until resolution to Grade \leq 1 or baseline Follow complete blood count (CBC) at least every 7 days If resolution to Grade \leq 1 or baseline occurs \leq 8 days, reintroduce CC-122 at the same dose level If AE resolution occurs $>$ 8 days, or event occurs within the same cycle, reintroduce CC-122 at the lower dose level, if available
Grade 4 thrombocytopenia	
 Hold CC-122 until recovery to Grade \leq 1 or baseline Repeat CBC within 24 to 48 hours Follow CBC at least every 7 days Reintroduce CC-122 at the lower dose level, if available
Grade 3 neutropenia	
 Hold until resolution to Grade \leq 1 Follow CBC at least every 7 days If AE resolution to Grade \leq 1 occurs \leq 8 days, reintroduce CC-122 at the same dose level If AE resolution occurs $>$ 8 days, or event occurs within the same cycle, reintroduce CC-122 at one dose level lower, if available
Grade 4 neutropenia	
 Grade 4: Hold CC-122 until recovery to Grade \leq 1 Follow CBC at least every 5 days Reintroduce CC-122 at the lower dose level, if available Use of growth factors (G-CSF, GM-CSF) is permitted at the discretion of the Investigator
Febrile neutropenia	
 Hold further dosing until recovery to Grade \leq 1 then resume dosing CC-122 at one dose level lower, if available Use of growth factors (G-CSF, GM-CSF) is permitted at the discretion of the Investigator
Any hematological toxicity requiring interruption for $>$ 3 weeks	
 Discontinue CC-122

AE = adverse event; CBC = complete blood count; G-CSF = granulocyte-colony stimulating factor; GM-CSF = granulocyte-macrophage colony stimulating factor.

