1. JUSTIFICATION FOR AMENDMENT

Significant changes included in this amendment are summarized below:

1. Per Food and Drug Administration (FDA) request on Investigator Brochure (IB) Edition 9, protocol was updated to include standard Cytochrome P450 (CYP) interaction language in alignment with all CC-122 studies.

Revised Sections: 8.2.

2. Updates to exclusion criteria.

Exclusion criteria #1 was updated to exclude all subjects who have had prior treatment with regorafenib. This change is based on the recent FDA approval of regorafenib for hepatocellular carcinoma (HCC) in the second line setting in order to maintain the homogeneity of the patient population.

Exclusion criteria #3 was updated to exclude any subjects with systemic therapy in the 4 weeks prior to starting investigational product in order to allow for an appropriate wash out period for any prior therapies.

Exclusion criteria #15h was changed from >100 pg/mL to >300 pg/mL to allow for inclusion of subjects with brain natriuretic peptide (BNP) between 100-300 pg/mL with cardiologist evaluation (specified under section 15.h.a). This change was made to allow subjects at low cardiac risk to be enrolled in the trial despite slightly elevated BNP. This language was updated in alignment with existing wording in other CC-122 protocols (eg, CC-122-ST-001).

Revised Sections: 4.3.

3. Due to the incidence of rash (and subsequent dose limiting toxicities) observed during the dose escalation portion of the study, language was added to the protocol to provide guidelines on the management of Grade 1 and Grade 2 rash. Rash is known to be a potential overlapping toxicity between CC-122 and nivolumab and these guidelines are being implemented to help mitigate the risk of these rashes reaching Grade 3 or higher.

Revised Sections: Table 6, Table 8, 7.10.4.8 (added).

4. Per Celgene protocol template and Informed Consent Form (ICF) template, updates to pregnancy language as defined by Drug Safety for teratogenic compounds (including CC-122).

Revised Sections: 10.4, 10.4.1, 10.4.2.

Minor changes included in this amendment are summarized below:

Minor editorial changes throughout.

Revised Sections: Global

Addition of Celgene Therapeutic Area Head name and Title.

Revised Section: Celgene Therapeutic Area Head Signature Page

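### Table 6 of the protocol: the restart bullets for Grade 3 rash can send the same event both to the same and to a lower CC-122 dose

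*Protocol*

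**What the plan says.** Three bullets in the same Table 6 entry (Protocol Section 7.10, rash of Grade 3 or worse) govern the hold and the restart of CC-122:

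- Hold: "If Grade 3 hold CC-122 until recovery to Grade ≤ 1".
- Same dose: "If AE resolution to Grade ≤ 1 occurs ≤ 8 days, reintroduce CC-122 at the same dose level".
- Lower dose: "If AE resolution to Grade ≤ 2 or > 7 days, reintroduce CC-122 on lower level, if available".

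Other bullets in the entry call for CC-122 to be discontinued after a second rash of Grade 3 or worse, for a desquamating Grade 3 rash, and for any Grade 4 rash. A further bullet, on certain rash types lasting up to 7 days, speaks of medical management and gives no restart dose.

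Table 5 (Section 7.9) sets the step down: 4.0 to 3.0 mg, 3.0 to 2.0 mg, 2.0 to 1.0 mg, and nothing below 1.0 mg.

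Two sections tie dose reduction to DLTs. Section 7.6 lists "Any toxicity that would lead to dose reduction or discontinuation of CC-122 or discontinuation of nivolumab during Cycle 1". Section 7.9 says that a treatment-related toxicity leading to such a change "that occurs in Cycle 1 during dose escalation will constitute DLT".

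**The concern.** A dose-modification rule should give one answer for one event. Here the two day limits overlap, the two grade limits are nested and joined by an or, and the recovery grade for restart differs from the grade that ends the hold. Two sites following the text could restart the same kind of event one dose level apart, and each could point to a bullet in support.

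The first thing at stake is the safety of the subject being re-dosed, because a second rash of this severity ends CC-122 treatment. The second is the meaning of the exposure tables. The SAP reports relative dose intensity (Section 9.9), CC-122 dose reductions and time to first reduction (Section 9.10), and adverse events leading to reduction (Section 11.1.1). Part of the variation in those summaries could reflect which bullet a site followed.

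Rash is not a remote possibility in this trial. The justification for the amendment refers to rash in these words: "Due to the incidence of rash (and subsequent dose limiting toxicities) observed during the dose escalation portion of the study".

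**Working it through.** The plan states no figure to reproduce, so the check is of the rule logic.

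**Inputs.** Let g be the grade at resolution (0, 1 or 2) and d the whole days to resolution (1 to 28). All conditions come from the Table 6 entry.

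- Same dose (A): g ≤ 1 and d ≤ 8. This gives 2 grades × 8 days = 16 combinations.
- Lower dose (B): the bullet names g ≤ 2 and d > 7, joined by an or. Four readings were tried.

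| Reading of B | Condition | A combinations that also meet B |
|---|---|---|
| Literal | g ≤ 2 or d > 7 | 16 of 16 (days 1 to 8) |
| Or taken as and | g ≤ 2 and d > 7 | 2 of 16 (day 8) |
| Charitable | g = 2, or g ≤ 1 with d > 7 | 2 of 16 (day 8) |
| Time only | d > 7 | 2 of 16 (day 8) |
| Comparator: Table 7 day limit | d > 8 | 0 of 16 |

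**Step 1, the day limits.** A runs through day 8 and B starts after day 7, so both hold for recovery to Grade 0 or 1 on day 8. These are the 2 combinations that remain in each non-literal reading.

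**Step 2, the or.** Every g ≤ 1 is also g ≤ 2. Read literally, a rash at Grade 1 on day 4 meets A, and it meets B on grade alone. The same-dose bullet is left with no case of its own.

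**Step 3, the recovery grade.** B describes reintroduction after resolution to Grade 2 or less. The hold bullet ends only at Grade 1 or less. A rash that has improved to Grade 2 and stayed there is still on hold under one bullet and eligible for restart under the other.

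**Comparator.** For Grade 3 neutropenia and Grade 3 thrombocytopenia, Table 7 pairs up to 8 days (same dose) with more than 8 days (lower dose), so those day limits do not overlap. The comparison is of day limits only. Table 7's lower-dose bullet has a further same-cycle trigger, which is set aside here.

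**Size of one step (Table 5).** (2.0 − 1.0)/2.0 = 50%; (3.0 − 2.0)/3.0 = 33%; (4.0 − 3.0)/4.0 = 25%. This is how far apart two restarts of the same event could be. It is not an estimate of any effect on results.

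**DLT status.** Section 7.6 separately makes a clinically relevant non-hematologic toxicity of Grade 3 or worse a DLT, and rash is not among the exceptions. Such a rash in Cycle 1 therefore normally counts whichever dose is resumed. The restart bullet could decide the matter only where the rash does not already meet another DLT criterion, for example because it is judged not clinically relevant.

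**The case against.** **Reach.** A reader might infer that every Grade 3 rash resolving within 8 days faces two instructions. The documents do not support that. Desquamating rash and second occurrences lead to discontinuation, and a subject at 1.0 mg has no lower level. The literal reading is also an unlikely intention, since it empties the same-dose bullet. This stands, and it limits the conflict to a first, non-desquamating Grade 3 rash with a lower level available. The day-8 overlap survives it.

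**A reading without overlap.** One could take the lower-dose bullet to mean exactly Grade 2 and more than 7 days. That changes both the inequality and the connective, leaves recovery to Grade 1 after day 8 with no instruction, and still conflicts with the hold bullet. It is a rewrite rather than a reading.

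**Discretion.** Table 6 is a set of guidelines, Section 7.9 lets the investigator reduce CC-122 on the basis of Section 7.10, and Section 7.12 allows restart at the same or a reduced dose. So neither dose is generally prohibited. But both sections refer back to Section 7.10, which holds the conflict. Where Table 6 intends a choice, as for troponin elevation and other toxicities of Grade 3 or worse, it says so; the rash bullets give two directives. Section 7.10.4.8 asks for interruption at Grade 3 and gives no restart dose.

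**DLTs and the amendment.** A reader might infer that the ambiguity distorts DLT counts, or that the amendment was written to control this rule. Neither is supported. Section 7.6 normally captures the event already. The amendment's rash item is one of four significant changes and describes guidance for Grades 1 and 2. It does not say that the Grade 3 restart bullets were written or revised then.

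**Consequences.** The SAP derives exposure from doses given or assigned, so the summaries remain computable, and they are descriptive. SAP Section 15 says the expansion will not go ahead, which reduces further exposure to the rule. Both points stand. They lower the stakes without giving the entry a single answer.

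**Conclusion.** The entry is wrong as written: one event can meet two different restart instructions, and the grade for restart disagrees with the grade that ends the hold. The overlap covers all 16 same-dose combinations on the literal reading and 2 of 16 on each of the three other readings tried. These are combinations of grade and day, not subjects. The documents give no count of rashes affected and do not show that sites did re-dose differently, so the consequence is a possibility, not a finding.

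The conclusion rests on the current wording of Table 6 and on counting days to resolution as whole days. In continuous time, the day-8 overlap is recovery to Grade 1 or less after more than 7 and up to 8 days. The point deserves correction because it is a dosing instruction for a toxicity seen in this trial, with a secondary bearing on the exposure summaries.

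**What to change.** The sponsor should reconcile the three bullets so that each combination of recovery grade and days to recovery leads to exactly one action. That means day limits that do not overlap, a single recovery grade for restart that agrees with the hold bullet, and no ambiguous or. Which limits and which grade to use is a clinical decision for the sponsor, and none is proposed here.

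The text change is short, but it alters a dosing instruction and so would go through a protocol amendment. Under Protocol Section 13.5, that needs written ethics approval before implementation unless the change counts as administrative. No analysis changes.
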